2.2 Secondary Objective(s)

- Patient and surgeon satisfaction using the scar assessment scale (POSAS) developed and previously published by Draaijers et al.
- Treatment related adverse events. Examples are pain, skin thinning, color/texture change, atrophy, telangiectasis, infection and erythema.
- Early post-operative complications (within 2 weeks of surgery). Example of that are wound dehiscence, graft necrosis, infection, bleeding, partial/complete graft failure and/or ectropion.

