9. ADVERSE EVENT RECORDING AND REPORTING

9.1 Recording Requirements

- Research subjects will be routinely questioned about treatment related adverse events at each study visit. All possible, if any, non-serious examples are pain, erythema/redness, skin thinning/atrophy, infection, color/texture change, swelling, telangiectasia, graft shrinkage/rejection and need for additional surgery. Serious adverse events are not expected to be seen at any moment of the study since medication has been shown to be safe to the patient. In addition, patients will be evaluated for early post-operative complications (within 2 weeks of surgery) not related to study drug treatment. Example of that are wound dehiscence, graft necrosis, infection, bleeding, partial/complete graft failure and/or ectropion. Events will be followed until it resolves or stabilizes; if needed other treatment (eg. antibiotics) will be added to manage adverse event.

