### 10.1 Primary endpoint or outcome measure

- The primary endpoint will be graft size change. Graft shrinkage will be evaluated by measuring the graft before and after surgery (at each post-operative visit) to estimate the contraction with or without treatment.

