### 10.2 Secondary endpoints or outcome measure(s)

- The secondary endpoints that will be measured during the clinical study are patient and surgeon satisfaction using the scar assessment scale (POSAS) developed and previously published by Draaijers et al., treatment related adverse events, and early post-operative complications.

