#### **10.6 Safety Analysis**

- The safety analysis of the study drug is our secondary endpoint that will be analyze with a sample t-test using a level of significance of 0.050.

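### Graft shrinkage, the primary efficacy outcome, and re-operation are also listed as treatment-related adverse events, so a pooled safety test could mask 5-FU injection reactions

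*Protocol*

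**What the plan says.** Protocol 9.1 sets the recording rule: "Research subjects will be routinely questioned about treatment related adverse events at each study visit". Its possible non-serious examples end with "telangiectasia, graft shrinkage/rejection and need for additional surgery". Protocol 2.2 gives a shorter list for the same secondary objective: "Examples are pain, skin thinning, color/texture change, atrophy, telangiectasis, infection and erythema".

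SAP 10.1 makes the same outcome the efficacy endpoint: "The primary endpoint will be graft size change. Graft shrinkage will be evaluated by measuring the graft before and after surgery". Protocol 1.1 names scarring and shrinkage as the commonest complication of these grafts and says that a further operation can follow from it.

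SAP 10.2 counts "treatment related adverse events, and early post-operative complications" among the secondary endpoints. SAP 10.6 then states: "The safety analysis of the study drug is our secondary endpoint that will be analyze with a sample t-test", at the 0.050 level. It does not say what is tested: an event count, an any-event indicator, or each event type separately. No section sets a threshold at which shrinkage becomes an adverse event, or separates failure of effect from reactions to the injection.

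**The concern.** The safety comparison should show what harm the 5-FU injection adds to a saline injection. The trial's hypothesis is that 5-FU reduces shrinkage. If that is true, shrinkage events, and the operations that follow from them, will collect in the saline arm. Counted as treatment-related adverse events, they raise the comparator's total and offset real 5-FU reactions such as pain, atrophy or telangiectasia. The better the drug works, the stronger the offset. Masking does not protect against this, because the imbalance comes from a true effect and not from biased reporting.

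At stake is how a statement such as no more adverse events than saline is read. With up to 15 patients per arm, a few shrinkage events could produce that statement through efficacy alone.

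**Working it through.** **The plan's own figure.** SAP 10.3 gives a difference of 13.2 (read here as percentage points), SD 10, two-sided alpha 0.050, 80% power and 20 patients in total. By the normal approximation, n per arm = 2 × (1.960 + 0.842)² × (10/13.2)² = 9.01, rounded up to 10. The exact noncentral t power at 10 per arm is 79.7%. The stated 20 is reproduced, so the design effect of 13.2/10 = 1.32 SD can be used below.

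**How far shrinkage events can differ.** Assume that shrinkage is Normal with SD 10 in both arms, with a mean 13.2 points lower on 5-FU, and that shrinkage above a threshold is recorded as an event. The gap in event rates is largest with the threshold midway between the means: 2Φ(0.66) − 1 = 0.49. The design effect alone can therefore put 49 points more shrinkage events on saline.

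**Effect on a pooled variable.** Let r be the proportion of patients with an injection reaction and s the proportion with a shrinkage event, independent of each other.

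- Any event: P = 1 − (1 − r)(1 − s).
- Mean count: r + s. The difference between arms reverses once the shrinkage gap exceeds the reaction gap.

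Assumed inputs, none given in the documents: control mean shrinkage 20%, 25% or 30%; threshold 10%, 20% or 30%; reactions 20% on saline against 40% or 60% on 5-FU. The result depends only on the control mean minus the threshold, so the nine combinations give seven distinct rows. The rows for 0 and 10 each stand for two combinations.

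| Control mean minus threshold | Shrinkage events, saline v 5-FU | Any event, saline v 5-FU (reactions 20% v 40%) | Difference, 20% v 40% | Difference, 20% v 60% |
|---|---|---|---|---|
| −10 | 16% v 1% | 32.7% v 40.6% | +7.9 | +27.7 |
| −5 | 31% v 3% | 44.7% v 42.1% | −2.6 | +16.7 |
| 0 | 50% v 9% | 60.0% v 45.6% | −14.4 | +3.7 |
| 5 | 69% v 21% | 75.3% v 52.4% | −23.0 | −7.1 |
| 10 | 84% v 37% | 87.3% v 62.5% | −24.8 | −12.3 |
| 15 | 93% v 57% | 94.7% v 74.3% | −20.4 | −11.8 |
| 20 | 98% v 75% | 98.2% v 85.1% | −13.1 | −8.1 |

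Differences are 5-FU minus saline in percentage points, from unrounded rates. The true excess of reactions is +20 in the fourth column and +40 in the fifth.

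Worked row (control mean 25%, threshold 20%): on saline s = 1 − Φ(−0.5) = 0.69; on 5-FU the mean is 11.8% and s = 1 − Φ(0.82) = 0.21. Any event on saline is 1 − 0.80 × 0.309 = 0.753, and on 5-FU it is 1 − 0.60 × 0.794 = 0.524. The mean count also reverses, from +0.20 to −0.29 events per patient.

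**Reading.** With reactions at 20% v 40%, the excess reverses in eight of nine combinations and shrinks to 8 points in the ninth. At 20% v 60%, it reverses in five of nine, and the difference runs from −12 to +28. In every row the excess is understated. These fractions describe the assumed grid; they are not probabilities. Re-operation is not modelled. Where it follows from shrinkage, counting it would push in the same direction.

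**The case against.** The strongest reply is that masking needs pooling, and SAP 10.6 does not define a pooled variable. If each event type were reported separately, the offset would disappear. This stands, and it makes the point conditional. A reader might infer that the plan contains an any-event composite; it does not. But a single t-test for safety needs one number per patient, and the SAP plans no tabulation by type, so nothing in the text prevents pooling.

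Four other readings are tempting and are not supported:

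- That sites must record all contraction on saline as treatment-related. Protocol 9.1 gives possible examples, does not waive the judgement of relatedness, and deals separately with early complications unrelated to the study drug. Misattribution is possible under masking; it is not instructed.
- That shrinkage is the normal course of a graft. Protocol 1.1 calls it the commonest complication, and listing a known complication as a possible adverse event is consistent with that.
- That 2.2 and 9.1 contradict each other. Both lists are examples, and 2.2 also omits swelling, which 9.1 includes.
- That recording one outcome under both efficacy and safety is an error in itself. No analysis adds the two together.

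A further objection concerns the remedy. Taking graft events out of safety could hide harm: Protocol 13.2 stops the study if treatment proves harmful to the graft, and the primary test is two-sided. This stands, and it limits what may be moved. Rejection is not the efficacy endpoint, and surgery for an injection complication is a safety event.

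Finally, the safety test is weak in any case. At 15 per arm, 3 patients against 1 with a reaction gives a two-sided Fisher p of about 0.60 even with shrinkage left out. That is true, so the practical damage is to the direction and totals that readers will see more than to a significance decision.

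**Conclusion.** The overlap between the efficacy endpoint and the adverse event list is in the text and is certain. Its consequence is conditional. If the safety variable is a count or an any-event indicator, lack of effect on saline can reduce, cancel or reverse a true excess of 5-FU reactions. At the planned effect the offset can reach 49 points in the shrinkage-event rate. The illustrated results rest on assumed control shrinkage, an assumed threshold, assumed reaction rates and independence. A reader might infer that 5-FU will look safer than saline. The documents do not support that: with a large enough reaction excess, or a high threshold for calling shrinkage an event, the excess stays visible though smaller. The point is worth correcting before unmasking, because safety is a stated objective and the correction is cheap.

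**What to change.** In Protocol 9.1 and SAP 10.6:

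- Keep recording all the listed events at every visit.
- Define the treatment-related adverse event variable explicitly, without graft shrinkage and without re-operation done for shrinkage. Show those two by arm in their own rows.
- Keep graft rejection, graft loss and surgery for an injection complication in the safety endpoint.
- Tabulate adverse events by type and arm.
- Leave reporting under Protocol 9.2 and the review of harm to the graft under Protocol 13.2 as they are.

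The cost is a few sentences in the two sections, with no new visits or measurements. There are two downsides. The headline adverse event total no longer includes shrinkage, although shrinkage is still shown. And the cause of each re-operation has to be judged and noted while the treatment is still masked.

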9.2 REPORTING PROCEDURES

- **Reporting Adverse Events to the Human Studies Committee (HSC)**
- Will follow HSC Policy for “Reporting Adverse Events and Unanticipated Problem”. As follows, any adverse events that are serious, unexpected and related or possibly related to the study will be reported to the HSC within 7 days from the time the PI becomes aware of the event. Any unexpected and study-related death will be reported to HSC within 24 hours of the PI’s knowledge of the event by e-mail or telephone. A completed AE report form will be submitted to HSC within 7 calendar days of initial HSC notification. If the PI becomes aware more than 30 days after the conclusion of a subject’s participation of a serious adverse event that is both related to the research and unexpected, the PI will

report the event to HSC at the time he becomes aware of it. PI will report to the HSC all non-serious adverse events that are unexpected and related or possibly related to the research within 30 calendar days from the time the PI becomes aware of the event. All unanticipated problems (UAP) involving risks to subjects or others will be reported in writing to the HSC within 7 calendar days from the time the PI becomes aware of the event. If a UAP or an unexpected serious adverse event results in a subject's death or was potentially life-threatening, the PI will notify HSC through e-mail or phone within 24 hours from the time the event is identified. A follow-up report will be submitted at a later date when more information is available. The PI will notify HSC through e-mail or phone within 24 hours from the time the event is identified for UAPs that take the form of a data loss.

9.3 Withdrawal of Subjects due to Adverse Events

- If subject presents with a serious event from intervention, he/she will be withdrawn from further study intervention and the investigators will evaluate the reason for event. If patient states a minor adverse event patient will continue unless patient wishes to voluntary withdraw.
- A serious event includes a severe allergic reaction to medication causing systemic symptoms of anaphylaxis.
- Data will continue to be collected from the withdrawn subjects, until 12 months after original surgery date, but without further intervention (no more injections) and patient will not be included in the analysis.

Withdrawn subjects from study participation due to an adverse event will not be replaced for a new patient.

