5. STUDY DRUG(S)/DEVICE(S)

5.1 Study Drug Information

- Study drug that will be administered to fifteen of our patients is 5-Fluorouracil, FDA-approved systemic chemotherapy medication to treat certain cancers, the concentration 50 mg/ml and will inject less than 1cc total in the subcutaneous tissue of the affected area.
- Study placebo that will be administered to the other fifteen of our patients is sodium chloride 0.9% (PF).
- Medications will be given every 2 to 3 weeks for a total of 4 injections.
- The amount of medication injected will depend on the extension/dimension of the periocular area affected with a maximum dose of 1cc total.

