13. STUDY DISCONTINUATION CRITERIA

13.1 Discontinuation of Individual Research Subjects

- Discontinuation criteria for individual research subjects has been previously addressed under section 5.2 (Withdrawal of subjects due to non-compliance/adherence) and section 9.3 (Withdrawal of subjects due to adverse events) of the clinical protocol. Decision will be done by PI. Data will be collected until subjects are withdrawn. If subjects have already received part of the treatment or withdrawn before treatment has been started then subjects will be replaced using the same eligibility criteria.

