### 10.3 Sample Size Determination

- The plan number of subjects to be enrolled into the clinical study is up to 15 for the treatment group and up to 15 for the placebo group. A total sample size of 20 patients is needed to achieve a 80% power to detect a difference of at least 13.2% less than the control in mean changes in graft size from pre-treatment (2-3 weeks post-operative date) to the last follow up with a standard deviation of 10% (common to both groups) and with a significant level (alpha) of 0.050 using a two-sided two-sample equal-variance t-test. If we take into account a 20% dropout rate out of 20 patients, then 12 patients are needed to be enrolled into each arm of the study. For that reason, 15 patients are going to be enrolled but statistical analysis can be done once 10 patients in each arm have completed the study. Determined with the help of [name] at MGH biostatistics department.

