### 10.4 Analysis Population (if applicable)

- Independent sample t-test will be applied to the primary outcome analysis (i.e., comparison of mean changes in graft size from pre-treatment to the last follow up). In addition, for the secondary outcome we will utilize repeatedly measured POSAS scores over time by using longitudinal linear mixed effects model which can further determine the time dependency of the treatment effect. The model will include treatment group (group 0 for placebo and 1 for treatment), time (0=two-three weeks post-op visit / first injection, 1=second injection, 2=third injection, 3=fourth injection, 4=two to three weeks after last injection), and group x time. Both effects (1. group difference in the pre-treatment measurement 2. time trend of the control) will be considered fixed effects and the individual 2-3 weeks post-operative measurement random. Group x time effect is expected to be an increased slope of the treatment group over time. For the other outcome measurements, we will apply the same methods. Also statistical methods will include intention to treat (ITT) analysis to compare all subjects in the groups randomly assigned. We will exclude anyone who gets partial treatment, exit early or is lost to follow up; in those cases we will replace patient with another subject that meets the criteria. Discussed with [name] at MGH biostatistics.

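### Protocol 9.3 says adverse-event withdrawals are not replaced, while Protocol 13.1 and SAP 10.4 replace them without exception; one rule is needed, and withdrawn patients should stay in the analysis

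*Protocol*

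**What the plan says.** Four sections deal with replacement.

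- Protocol 9.3, on adverse events: "Withdrawn subjects from study participation due to an adverse event will not be replaced for a new patient". The same section keeps collecting data on these patients until 12 months after surgery, but leaves them out of the analysis.
- Protocol 13.1, on discontinuation in general, refers back to 5.2 and to "section 9.3 (Withdrawal of subjects due to adverse events) of the clinical protocol". It then states: "If subjects have already received part of the treatment or withdrawn before treatment has been started then subjects will be replaced". It also says that data collection ends at withdrawal.
- SAP 10.4: "We will exclude anyone who gets partial treatment, exit early or is lost to follow up", followed by "in those cases we will replace patient with another subject that meets the criteria". The sentence just before these promises an intention-to-treat analysis of all subjects as randomised.
- Protocol 5.2: patients withdrawn for non-compliance are replaced, and the replacement receives the corresponding medication.

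On numbers, SAP 10.3 plans up to 15 per arm and says that "statistical analysis can be done once 10 patients in each arm have completed the study". Protocol 5.1 has the same count: "Study drug that will be administered to fifteen of our patients is 5-Fluorouracil". Protocol 3.2.3 has the pharmacy disclose the study drug when a participant has a serious adverse event.

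**The concern.** A patient withdrawn for an adverse event after the first, second or third injection, with more planned, has received part of the treatment. Under 9.3 that patient is not replaced; under 13.1 and 10.4 the patient is. No section says which governs, so the plan cannot be followed as written.

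Three things are at stake. First, 9.3 and 10.4 both remove these patients from the analysis, so the replacement rule directly sets the analysed arm sizes. Second, Protocol 13.1 leaves discontinuation decisions to the principal investigator. With the rule undefined, the choice could be made after the event and, for a serious event, after the arm has been disclosed. Third, if 9.3 is followed while 5.2 stands, replacement depends on the reason for leaving: non-compliers are refilled and adverse-event patients are not.

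**Working it through.** **The rules side by side, for an adverse-event withdrawal**

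| Time of withdrawal | 9.3 | 13.1 | 10.4 |
|---|---|---|---|
| Before the first injection | not replaced | replaced | replaced, if this counts as early exit |
| After injection 1, 2 or 3 | not replaced | replaced | replaced |
| After injection 4 | not replaced | silent (not partly treated) | replaced, if this counts as early exit |

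The middle row is a direct contradiction in both documents. The first row conflicts with 13.1. The last conflicts only on one reading of 10.4.

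**Inputs (SAP 10.3).** Difference 13.2 percentage points, common SD 10, two-sided alpha 0.05, equal-variance t-test, 20% dropout, up to 15 enrolled per arm, 10 completers per arm needed.

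**The plan's own figure.** The noncentrality is 13.2 / (10 × √(1/n1 + 1/n2)) on n1 + n2 − 2 degrees of freedom. For 10 v 10 this is 1.32 / 0.447 = 2.95 on 18 df, and the power is 79.7%. The stated 20 patients for 80% power reproduce. The stated 12 per arm is 10 × 1.2; dividing by the retention rate gives 10 / 0.8 = 12.5, so 13. Fifteen covers either.

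**Effect of the replacement rule on power.** At 20% dropout, 15 × 0.8 = 12 per arm remain. The number of further adverse-event exclusions is an assumption, because the documents give none.

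| Situation | Analysed | Noncentrality (df) | Power |
|---|---|---|---|
| No losses, or all replaced | 15 v 15 | 3.62 (28) | 93.7% |
| 3 unreplaced in one arm, no other loss | 12 v 15 | 3.41 (25) | 90.6% |
| 20% dropout | 12 v 12 | 3.23 (22) | 87.1% |
| 20% dropout and 2 more from 5-FU | 10 v 12 | 3.08 (20) | 83.4% |
| 20% dropout and 3 more from 5-FU | 9 v 12 | 2.99 (19) | 81.0% |

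The last row has power above 80% but falls below the plan's own trigger of 10 completers in each arm.

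**Chance of a shortfall if nobody is replaced.** An arm of 15 keeps at least 10 completers if it loses no more than 5. With losses independent and equally likely in both arms, P(Bin(15, 0.20) ≤ 5) = 0.939. For both arms this is 0.939² = 0.882, so the chance that at least one arm falls short is 1 − 0.882, about 12%. The same calculation gives 27% at an assumed 25% dropout and 48% at an assumed 30%.

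**The case against.** The best defence is that 9.3 is the specific rule and 13.1 the general one, and that 13.1 defers to 9.3 by citing it. That reading is available. It is not secure: 13.1 cites 9.3 and then states its replacement rule with no exception, and 10.4 does not mention 9.3 at all. A reader still has to guess.

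A second defence is that few patients will be affected. Under 9.3 only a serious event forces withdrawal, and a patient with a minor event leaves only by choice. Protocol 9.1 expects no serious events, and the retrospective series of 19 patients cited in Protocol 1.2 reported no complications. This stands as a limit on size. The number could be zero, but the plan still needs a usable rule if it is not.

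A third is that 5.2 does not contradict 9.3, and that enrolment above 15 in an arm can arise from 5.2 replacements too. Both statements are correct. Aligning 5.2 is a design choice, made so that replacement does not depend on the reason for leaving.

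A reader might also infer more than the documents support:

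- That 9.3 depletes the 5-FU arm. No section gives event or withdrawal rates by arm, so greater loss on 5-FU is plausible but undocumented.
- That adverse-event losses should be subtracted from 10 v 10, which puts power well below 80%. Ten per arm is the count of completers, and a withdrawn, excluded patient is not one. The subtraction starts from the up to 15 enrolled.
- That sites could apply different rules. The documents describe one centre, with the principal investigator deciding.
- That every withdrawal after an injection meets the conflict in 13.1. A withdrawal after the fourth injection does not.

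**Conclusion.** The contradiction is certain and rests on the text alone. Adverse-event withdrawals that are partly treated, and under 13.1 also untreated ones, are subject to opposite replacement rules with no precedence stated. The choice could be made with the arm known after a serious event; the documents do not say that it would be, nor do they keep the person deciding on replacement masked.

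The numerical effect is modest. On the plan's own effect size, SD and 20% dropout, power stays between 81.0% and 87.1% with up to three further exclusions from one arm. Replacement is not needed for the stated power in expectation, because up to 15 are enrolled to obtain 10.

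Settling replacement alone would not be enough. Selective removal of patients comes from the exclusion wording in 9.3 and 10.4, which conflicts with the intention-to-treat statement in 10.4 whichever replacement rule is chosen.

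**What to change.** 1. State one rule in Protocol 9.3, Protocol 13.1 and SAP 10.4, and align Protocol 5.2 with it: *No randomised patient is replaced, whatever the reason or arm; up to 15 per arm are enrolled to allow for losses.* Remove the replacement sentences in 5.2, 13.1 and 10.4.
2. Delete the clause in 9.3 that leaves adverse-event withdrawals out of the analysis, and the sentence in 10.4 beginning "We will exclude anyone who gets partial treatment, exit early or is lost to follow up". Withdrawn patients, whom 9.3 already follows to 12 months, are then analysed in their randomised arm under the stated intention-to-treat analysis.
3. Reconcile 13.1, which ends data collection at withdrawal, with 9.3, which continues it.

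The cost is wording in four sections, and recruitment is capped at 15 per arm. There are two downsides. Without replacement, the chance that at least one arm has fewer than 10 completers is about 12% at 20% dropout, and it rises quickly if dropout is higher (27% at 25%, 48% at 30%, both assumed rates). And keeping partly treated patients in the comparison may dilute the observed difference, which is the usual price of intention to treat. Patients truly lost to follow-up will still lack a final measurement, so SAP 10.4 should say how they are handled.
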